17. Digital photograph(s) of all visible injected and non-injected tumor(s), and of any visible local reactions in or around the injected lesion(s). Photographs are required post-registration, Cycle 2 Day 7, Cycle 5 Day 1, Cycle 6 Day 7, Post-Treatment Safety Assessment, and Follow-Up Treatment Assessment visits, and ad hoc as the investigator deems necessary. Important guidelines regarding photographic methodology will be provided in a separate manual.
18. Intratumoral INXN-2001 [REDACTED] injection should be administered 3 hours \pm 30 minutes after the INXN-1001 dose. [REDACTED]
[REDACTED] Each subject will be carefully monitored for possible local reactions at the injection site and/or hypersensitivity reactions for at least 2 hours following the INXN-2001 injection. A detailed description of physical location(s) of the injected tumor(s) and surrounding tissue, and any visible local reactions will be documented. The [REDACTED]

19. The subjects will be dispensed INXN-1001 for self-administration after Day 1. The first INXN-1001 dose will be given at the clinical site in a fed state (within approximately 30 minutes after the start of a normal meal). The remaining 6 doses can be self-administered at the same time as on Day 1 (\pm 1 hour) in the fed state. Study sites must verify adherence with INXN-1001 dosing. Subjects should return bottles of INXN-1001 to the clinical site to determine extent of subject adherence to self-administration preferably on Day 7.
20. The following temporal sequences of drug administration for Arm A monotherapy and Arm C combination therapy will be followed:

For subjects enrolled in Arm C Ad-RTS-hIL-12 + palifosfamide Combination Therapy, the sequences for monotherapy + palifosfamide (sequences for Arms A + C) will be followed concurrently as shown above.

21. Day 1 clinical laboratory assessments may be performed within 15 days of the previous cycle through the Day 1 (prior to dosing) clinic visit. Clinical laboratory tests drawn for analysis prior to dosing on Day 15 of each cycle may be used for determining if the re-treatment criteria have been met, and must be reviewed by the investigator or designee prior to the next cycle of study drug administration. Repeat assessments may be obtained for those subjects with parameters \geq Grade 3.

- 22. Post-Treatment Safety Assessment visit will be performed 28 ± 3 days after the last dose of study drug or prior to receiving another anticancer therapy.

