A missed Day 2 or Day 3 study drug administration may be rescheduled to Day 4 of the same treatment cycle. If both Day 2 and Day 3 are missed, then only a single day may be rescheduled to Day 4 and the other will be skipped. In either case, the total duration of the treatment cycle should remain 21 ± 1 day by shortening the rest interval by 1 day. If the missed dose cannot be administered on Day 4, then it must be skipped and the subject should continue on protocol and take the next dose as originally planned.

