6.2.5 Retreatment Criteria, Dose Delays and Modifications

Subjects may receive up to 6 cycles of study drug treatment. To receive each repeat treatment cycle, all treatment-related AEs must have resolved to Grade 1 or baseline and the following laboratory criteria must be met:

Hemoglobin \geq 9 g/L	eGFR \geq 60 mL/min/1.73 m ²
Lymphocytes $>$ 700/ mm ³	AST and ALT \leq 2.5 x ULN For subjects with documented liver metastases, ALT and AST \leq 5 \times ULN
Neutrophils \geq 1,500/ mm ³	Total bilirubin $<$ 1.5 x ULN
Platelets \geq 100,000/ mm ³	INR and PTT $<$ 1.5 x ULN

Clinical laboratory tests drawn pre-treatment for analysis on Day 1 of each cycle may be used for determining if the re-treatment criteria have been met, and must be reviewed by the investigator or designee prior to the next cycle of study drug administration. Two treatment delays for recovery to acceptable levels are allowed at weekly intervals up to a maximum of 14 days. In the event that a treatment-related dose delay is necessary for palifosfamide, then the next cycle of study treatment will be administered at 80% of the dose ([Table 3](#)). If an AE is clearly related to 1 study drug and not the other (in combination Treatment Arm C), then dose modification/delay is to occur for the relevant study drug (INXN-1001 and/or palifosfamide). A maximum of two dose reductions, of either INXN-1001 or palifosfamide, will be allowed.

Table 3. Dose Modifications for Palifosfamide-related Toxicity^a

ADVERSE EVENT	PALIFOSFAMIDE
Hematologic	
Platelet count <100 × 10 ⁹ /L	Delay dose of palifosfamide up to 14 days until platelet count ≥ 100 × 10 ⁹ /L, then reduce by 20%.
ANC < 1500/mm ³	Delay dose of palifosfamide up to 14 days until ANC returns to ≥ 1500, then maintain dose when restarted.
Neutropenic fever	Delay dose of palifosfamide up to 14 days until resolved, then reduce by 20%.
Any Grade 4 hematologic toxicity	Delay dose of palifosfamide up to 14 days until Grade ≤ 1 or baseline, then reduce by 20%.
Estimated Glomerular Filtration Rate (eGFR) (Appendix 5)	
≥25% up to <50% decrease from baseline ^b	Hold dose until repeat test is performed. Reduce dose of palifosfamide by 20% if confirmed on repeat test.
≥50% decrease from baseline ²	Hold dose until repeat test is performed. Discontinue palifosfamide if confirmed on repeat test.
Non-hematologic (other than creatinine or urinary electrolyte wasting)	

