Not treatment-related Grade 3 if unresponsive to appropriate therapy.	Delay dose of palifosfamide for up to 14 days until Grade ≤ 1 or baseline, then reduce by 20%.
Not treatment-related Grade 4	Delay dose of palifosfamide up to 14 days until ≤ Grade 1 or baseline, then reduce by 20%.

^aWhen indicated, the maximum permitted delay of study drug administration due to toxicity and/or for confirmatory laboratory testing is 14 days.

^bBaseline eGFR determined based on the most recent serum creatinine measurement prior to study drug administration (ie, Cycle 1 Day 1 or Screening).

Subjects who experience a treatment-related Grade 4 AE, other than nausea and/or vomiting in the absence of optimal treatment with antiemetics, will be discontinued from study treatment. If, however, the subject has experienced a substantial benefit from treatment and the PI and Medical Monitor recommend continuation on the study, re-exposure to the experimental treatment may proceed on a case-by-case basis.

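### Footnote 21 lets a Day 15 blood test clear the next cycle, so a site can redose on laboratory values 5 to 9 days old with no later result required

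*Protocol*

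**What the plan says.** Section 6.2.5 is mandatory about the limits. For each repeat cycle, "all treatment-related AEs must have resolved to Grade 1 or baseline and the following laboratory criteria must be met"; the list covers hemoglobin, lymphocytes, neutrophils, platelets, eGFR, AST and ALT, bilirubin, INR and PTT. On which sample to use, it says: "Clinical laboratory tests drawn pre-treatment for analysis on Day 1 of each cycle may be used for determining if the re-treatment criteria" are satisfied.

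Footnote 21 is attached to the Day 1 column of Table 2B and does three things:

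- It moves the Day 1 draw: "Day 1 clinical laboratory assessments may be performed within 15 days of the previous cycle through the Day 1 (prior to dosing) clinic visit".
- It allows another draw to decide: "Clinical laboratory tests drawn for analysis prior to dosing on Day 15 of each cycle may be used for determining if the re-treatment criteria" are satisfied.
- It mentions a repeat test only as an option, from Grade 3 upward: "Repeat assessments may be obtained for those subjects with parameters" at that grade or worse.

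Both places require the investigator or a designee to review the results before the next cycle. Neither ranks the draws or limits the age of a qualifying value.

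**The concern.** The retreatment limits are a safety gate. They protect a subject only if the values reflect her condition when the dose is given. The Section 3.1 background states that the combination has not been studied in humans, and Section 6.2.4.4 asks for careful monitoring of electrolytes and hematologic toxicity with palifosfamide.

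If a site has a Day 1 platelet count below 100 × 10⁹/L, Table 3 delays palifosfamide whatever Day 15 showed. The exposure lies with a site that has a passing Day 15 panel and nothing later. Footnote 21 allows it to dose on time at 120 mg/m² even if a count, eGFR or liver value has since worsened. Arm A shares the retreatment limits, so the gap applies there too, although the Table 3 palifosfamide rules do not.

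**Working it through.** The plan states no maximum age, so there is no figure to reproduce. The check is day arithmetic.

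**Inputs**

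- Day 15 visit window ± 2 days (Tables 2A and 2B): the draw falls on Day 13 to Day 17.
- Cycle of 21 days (Synopsis, Section 4.1.1.1, Section 6.2.3): the next Day 1 is Day 22 of the current cycle. One sentence in Section 6.2.4.4 gives a 28-day palifosfamide cycle, but the same section later refers to the planned 21-day cycle, so 21 is used.
- Tolerance of 21 ± 1 day, stated only for rescheduled doses: "A missed Day 2 or Day 3 study drug administration may be rescheduled to Day 4 of the same treatment cycle".
- Delays: "Two treatment delays for recovery to acceptable levels are allowed at weekly intervals up to a maximum of 14 days".

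**Formula:** age at dosing = (day of next dose) − (day of draw).

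| Situation | Next dose on | Drawn Day 17 | Drawn Day 15 | Drawn Day 13 |
|---|---|---|---|---|
| Ordinary 21-day cycle | Day 22 | 22 − 17 = 5 | 22 − 15 = 7 | 22 − 13 = 9 |
| Rescheduled dose, 20-day cycle | Day 21 | 21 − 17 = 4 | 21 − 15 = 6 | 21 − 13 = 8 |
| Rescheduled dose, 22-day cycle | Day 23 | 23 − 17 = 6 | 23 − 15 = 8 | 23 − 13 = 10 |
| One weekly delay, nothing redrawn | Day 29 | 29 − 17 = 12 | 29 − 15 = 14 | 29 − 13 = 16 |
| Two weekly delays, nothing redrawn | Day 36 | 36 − 17 = 19 | 36 − 15 = 21 | 36 − 13 = 23 |

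The delay rows need a delay for a toxicity that is not a laboratory value. A delay for a failed laboratory value would itself imply a retest of that value.

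**Does anything force a later result?**

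- Table 2B schedules hematology and chemistry on Day 1, but footnote 21 sits on that column and lets the draw be earlier. If its first sentence means from Day 15 of the previous cycle onward, the Day 1 sample can be 22 − 15 = 7 days old.
- The review requirement fixes when someone must look at the results, not how old they may be.
- The repeat test is optional and starts at Grade 3. Section 6.2.5 implies that any failing value must later pass, but footnote 21 does not say so.
- Table 3 acts on a later value only if the site has one.

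None of these closes the gap.

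**The case against.** The best defense reads footnote 21 as one coherent laboratory window: tests may be drawn from about Day 15 up to dosing on Day 1, and Section 6.2.5 names the end of that window. What remains is a nominal 7 days against a shorter limit, and the length is the sponsor's choice. There are other controls: the limits stay mandatory, treatment-related adverse events must have settled, results must be reviewed, and physical examination, vital signs, ECOG status and ECG are done on Day 1. Harm is not shown. If counts are recovering in the third week, the Day 15 value is the stricter test. Much of the prior clinical experience is redacted and may hold a rationale for Day 15. Finally, the sentence speaks of dosing on Day 15, when no study drug is scheduled, so it may be a slip for Day 1.

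Much of this stands. Both provisions are permissive, and a reader who infers a contradiction between them goes further than the text. The direction and frequency of disagreement are unknown. But no listed control obliges a site to obtain a later laboratory result, and the bedside checks do not measure counts, eGFR or liver function. If Day 15 is a slip, the sentence still needs the same correction.

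Four stronger inferences are tempting but not supported:

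- **A 15-day look-back.** Counting 15 days back from Day 22 reaches Day 7, which would allow a Day 1 sample 15 days old. That reading is strained; a window opening on Day 15 fits the footnote better.
- **A wrongful dose cut.** A low Day 15 platelet count that recovers by Day 1 might seem to trigger 120 × 0.8 = 96 mg/m². Table 3 prescribes delay and then reduction, no dose is due on Day 15, and Section 6.2.5 ties the 80% dose to a necessary delay. For a low ANC, Table 3 keeps the dose.
- **A ranking rule already in the plan.** Table 3 footnote b, "eGFR determined based on the most recent serum creatinine measurement prior to study drug administration", defines the baseline eGFR. It does not rank retreatment draws.
- **A count of errors.** Five retreatment decisions per Arm C subject give 12 × 5 = 60 if the arm stops after Stage 1 and 26 × 5 = 130 if it completes. These are decisions if everyone completes six cycles, not doses given in error.

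**Conclusion.** The point holds as a gap in a safety gate. Footnote 21 expressly permits retreatment on a Day 15 ± 2 panel, and nothing in the protocol makes a later result govern or caps the age of the values. The size is 5 to 9 days in an ordinary cycle (nominally 7), 4 to 10 days where the ± 1 day tolerance applies, and 12 to 16 days after one weekly non-laboratory delay with nothing redrawn. This assumes a 21-day cycle and a site that uses the permission and has no later sample. It does not establish that any subject would be dosed wrongly, because the documents give no rate or direction of change between the two draws. A reader might also infer a threat to the 16-week PFS rate or its error rates. Nothing in the documents supports that: the endpoint and the stage rules do not depend on which draw is used. This is a cheap improvement for patient safety.

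**What to change.** In footnote 21 and Section 6.2.5:

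1. Delete the permission to decide retreatment on Day 15 tests.
2. State that the most recent result governs both retreatment and the Table 3 decisions, drawn on Day 1 before dosing or within a short fixed window before it. Three days is an example; the length is for the sponsor to set.
3. Require a redraw after any delay that goes beyond that window.
4. Require any value that fails the Section 6.2.5 limits to be repeated and to pass before dosing, in place of the optional repeat from Grade 3.

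The cost is wording in two places, plus an occasional later blood draw or a short wait for Day 1 results. Subjects already attend on Day 1, when hematology and chemistry are scheduled and the weight used for the palifosfamide dose is measured. Day 15 tests can continue as safety monitoring.

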3. INTRODUCTION

3.1 Disease Background (Recurrent/Metastatic Breast Cancer)

It is estimated that there are nearly 3 million women living in the United States with a history of invasive breast cancer, and an additional 226,870 women will be diagnosed in 2012.¹

Approximately 50% of women diagnosed with primary breast cancer will eventually relapse and develop metastatic or advanced disease. In addition, around 10% of patients present with metastatic disease at first diagnosis. The 5-year relative survival rate for women diagnosed with localized breast cancer is 98.6%; survival declines to 83.8% for regional stage and to 23.3% for distant stage. In addition to stage, factors that influence survival include tumor grade, hormone receptor status, and human epidermal growth factor receptor 2 (HER2) status.

Locoregional recurrence in breast cancer is an indicator of an aggressive tumor, and early recurrence carries a poor prognosis. Approximately 11 and 20 percent of patients treated with adjuvant therapies develop locoregional recurrence within 5 and 10 years, respectively.² If disease is localized, surgical excision can be attempted. Breast cancer recurrences after mastectomy pose a therapeutic challenge with few surgical options. Many patients have systemic disease either at the time of their cutaneous or other recurrence or soon after, some may manifest disease only at the dermal site of disease, and a few are cured with aggressive treatment. These lesions often are widespread throughout the chest wall or involve heavily irradiated tissue.

Recent advancements in targeted therapy and improvements in treatment have heralded a significant improvement in survival, but metastatic breast cancer remains essentially incurable. Advanced metastatic breast cancer may be treated with systemic therapy (chemotherapy, biological therapy, targeted therapy, hormonal therapy), local therapy (surgery, radiation therapy), or a combination of these treatments.³ Guidelines from the National Comprehensive Cancer Network for treatment of women with a locoregional breast cancer recurrence suggest consideration of systemic therapy after locoregional management, but do not specify the type of therapy or the duration.⁴ In case instant response is required, such as rapidly progressive, threatening disease or massive symptoms, combination cytostatic therapy is usually administered. Monotherapy is a choice for patients in whom a long-term stabilization of metastatic disease is the objective.

Almost all patients who have received first-line chemotherapy for their metastatic progression will relapse or progress and require subsequent treatment. For these patients requiring second- and subsequent-line therapy, the goals of treatment are to maintain a good quality of life and to prolong survival.⁵ Combination therapy is a mainstay of anticancer treatment, with optimal combinations producing synergistic antitumor responses, achieved by combining agents with non-overlapping mechanisms of action and safety profiles.

The addition of systemic chemotherapy (palifosfamide) to immunotherapy (Ad-RTS-hIL-12) in patients who are treated for a recurrence or metastasis of breast cancer may decrease the risk of a subsequent local recurrence or distant metastasis. This combination of therapeutic

agents has not yet been studied in human subjects, particularly in this disease; therefore, the safety profile is not yet clearly defined. The Phase II study proposed in this protocol (ATI001-201) will therefore examine the safety, antitumor activity, and immunological effects of intratumoral (IT) injections of INXN-2001 + orally administered INXN-1001 (Ad-RTS-hIL-12 monotherapy) alone and in combination with palifosfamide in subjects with advanced breast cancer.

[figure not shown]
11. *What is the best way to increase the number of people who use a particular service?*

For more information, contact the Office of the Vice President for Research and the Office of the Vice President for Student Affairs.

11. **What is the primary purpose of the *Journal of Clinical Endocrinology and Metabolism*?**

the first time in the history of the world, the people of the United States have been called upon to determine whether they will submit to the law of force, and let a一小部分 of their country be held at the point of a bayonet, or whether they will, in the language of their fathers, "put their souls in their hands and trust in God."

11. *What is the primary purpose of the following statement?*

3.3 Background and Rationale for Treatment Strategy

3.3.1 IL-12 Immunotherapy

Local cytokine delivery to tumors can induce a number of antitumor responses that include: 1) direct suppression of tumor cell proliferation, 2) induction of apoptosis, 3) antiangiogenesis, and 4) enhancement of local antitumor immune response. This enhancement of local antitumor response can be further characterized by cytokine-mediated activation of natural killer (NK) cells and cytotoxic T lymphocytes (CTLs), as well as the modulation of major histocompatibility molecule expression.¹⁰

Interleukin (IL)-12 is a potent immunostimulatory cytokine which activates and recruits dendritic cells (DC) that facilitate the cross-priming of tumor antigen-specific T cells. IL-12 functions as a key mediator for the generation of Th1 CD4+ effector T cells, activation of NK and CD8⁺ T cell cytotoxic activities, augmentation of antigen-specific antitumor responses, and the production of IFN- γ and TNF- α .¹¹⁻¹⁴ IL-12 also stimulates neutrophil and macrophage production of superoxides and nitric oxide, and induces the production of antiangiogenic factors by tumor cells. IL-12 has been shown to have antitumor activity in several animal models.

Clinical trials have been performed to assess the safety and efficacy of administering recombinant IL-12 protein to subjects with cancer, including, but not limited to, melanoma, renal cell carcinoma, colorectal, cervical, ovarian, and lung metastases. IL-12 protein was delivered via intravenous (IV), intraperitoneal (IP), or subcutaneous administration.¹⁵⁻²⁴ Systemic administration of IL-12 resulted in induction of systemic immune responses in some subjects, but there was limited clinical improvement and severe toxicity. In a Phase II trial evaluating repeated IV administrations of recombinant IL-12 in subjects with renal cell carcinoma, 12 of 17 subjects were hospitalized and 2 died due to hypovolemic shock. The study was halted, as most subjects experienced serious adverse events (SAEs) during the first cycle of treatment, and there was a high frequency of Grade 3 and 4 AEs, with 65% of subjects showing leukopenia and 47% showing hyperbilirubinemia and elevated aspartate transaminase (AST).²⁴ Based on reports to date, strategies for the local delivery of IL-12 through gene therapies may represent a safer and acceptable treatment approach in cancer patients.

It is therefore important to achieve the immunological benefits that IL-12 provides while avoiding the toxicity elicited by systemic delivery. IT delivery of Ad-RTS-hIL-12 accomplishes precisely this objective by allowing adjustment of IL-12 gene transcription by varying the dose of INXN-1001. The vector is localized in the tumor and the gene is produced locally in response to predetermined doses of the oral ligand. In this scenario the dose can be lowered if any toxicities are observed.

3.3.2 Palifosfamide

Palifosfamide is a potent, bi-functional, DNA alkylating agent that has activity in multiple tumors by evading typical resistance pathways. Palifosfamide is in the same class as bendamustine, cyclophosphamide, and ifosfamide. Palifosfamide is the functional active metabolite of ifosfamide (IFOS); however, palifosfamide has not been shown to cause toxicities observed with IFOS metabolites acrolein or chloracetaldehyde, such as hemorrhagic cystitis or neuropathy. The initial clinical development of palifosfamide focused on assessing the safety and tolerability of palifosfamide when administered as a single agent to subjects with advanced solid tumors. This approach was followed by Phase I through Phase III studies of palifosfamide in combination with doxorubicin as a potential treatment for advanced soft tissue sarcomas. An additional combination chemotherapy regimen of palifosfamide with etoposide + carboplatin is also being evaluated as a potential therapy for subjects with small cell lung cancer.

Palifosfamide is currently being investigated in a Phase III clinical trial. The MATISSE trial is evaluating palifosfamide ($130 \text{ mg/m}^2 \times 3$ q21 days) in combination with carboplatin and etoposide as a treatment for subjects with extensive-stage small cell lung cancer.

Digitized by [contact]

the *Journal of the American Statistical Association* (1990, 85, 130-139) and the *Journal of the Royal Statistical Society, Series B* (1991, 53, 371-384). The *Journal of the American Statistical Association* (1990, 85, 130-139) and the *Journal of the Royal Statistical Society, Series B* (1991, 53, 371-384).

10 of 10 pages

This image is a high-contrast, black-and-white scan of a document page. The content is heavily pixelated and obscured. A large, dark rectangular area occupies the upper portion of the page. Below this, there are several horizontal white bars of varying lengths. A few small black squares are located near the top left and middle left of the page. The right edge of the page shows a vertical white border, suggesting it is a scanned document page.

